The study design of TOHP is fairly complex, owing to the large number of diverse interventions being tested. The 10 clinical centers are each testing a different combination of interventions, although they can be divided into three broad categories: clinics offering only a combination of lifestyle interventions (sodium reduction, weight loss, and stress management, plus a control group); those offering only supplements (calcium and magnesium and their placebos in Stage 1, fish oil and potassium and their placebos in Stage 2); and "hybrid" clinics offering both types of intervention. Specific clinic allocations and the approximate numbers of subjects that will be assigned to each study group if recruitment goals are met are shown in Table 1.

For the lifestyle interventions, an open design is being utilized. After the initial orientation at randomization, those individuals assigned to the control

group will be invited to the clinic for data collection visits only. Because of this design feature, particular care will be taken to maintain blindness to intervention assignments among all clinic personnel involved in collecting any study data, especially BP. To avoid differential habituation to the BP measurement environment, data collection and intervention sessions should also take place in physically separate locations if at all possible. For the supplements interventions, placebo control has been adopted so that double blindness will be maintained.

ELIGIBILITY AND EXCLUSION CRITERIA

The general aim of the eligibility and exclusion criteria in TOHP is to assemble a group of healthy, non-hypertensive individuals who can safely undertake the study interventions and who are likely to be cooperative with follow-up requirements for the duration of the trial. In order to establish an overall study cohort that is generally comparable across all clinical centers, it is necessary to have generally uniform eligibility and exclusion criteria for all participants, regardless of which interventions an individual clinic may be testing.

Specific eligibility and exclusion criteria are outlined below.

Eligibility Criteria

1. Diastolic Blood Pressure

At each of the three screening visits, DBP will be determined as an average of all screening BPs obtained up to that time (three per visit), with the average falling within a specified range for a subject to be eligible. These ranges are:

Screening visit #1: DBP 75-97 mm Hg (3 readings)

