weight stratum. The numbers on these envelopes correspond to those on the randomization log maintained at the CC. If more than one participant is to be randomized at the same time, the clinic will arrange a listing of these subjects, first by weight stratum, if applicable, and then by ID order. The envelopes will then be opened in this order and the assignment communicated to each subject. Otherwise, randomization assignments are given in the order of the participants' appointments. Whenever a random assignment is made, the envelope, sealed (if the clinic staff obtained the subject's assignment from the CC) or unsealed (if the CC staff was unavailable), will be returned to the CC as confirmation of the randomization process. As further confirmation, the clinic will call the CC as soon as possible (usually the next working day) to report each intervention assignment made using the back-up system.

Once the assignment has been communicated to the participant, he or she is considered to be officially randomized, and every effort will be made to obtain complete follow-up information for the duration of the trial. Active intervention will begin at the discretion of the clinic; however, the target goal is to have all lifestyle participants attend their first intervention group meeting within 30 days of randomization. Any individual who fails to appear for his or her status review visit may be rescheduled for a new status review visit at the discretion of the clinic staff, as long as the visit is within 60 days of SV3.

2. Clinics Testing Supplements Only

At the conclusion of SV3, participants who are deemed provisionally eligible to continue in the trial will be given run-in calendar packs and a 24-hour urine kit and scheduled for a status review visit in four to eight weeks (28 to 56 days). All information necessary to assess eligibility will be sent to the CC for review and verification, and the CC will determine eligibility within 5 working days of receipt of SV3 data and send an eligibility status report to the clinic. The clinic will inform participants to discontinue their pills if their status is reported as ineligible and will take measures to clarify information if the CC reports an ambivalent status. Approximately 3-5 days in advance of their scheduled status review visit, eligible participants will be contacted to remind them of their appointment and instructed to bring their 24-hour

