Baseline and follow-up data, other than intervention-specific data, will be collected uniformly from all trial participants regardless of treatment assignment. Since adherence to the intervention regimens in TOHP may be problematic for participants, it is essential to collect data to assess compliance in the active intervention groups (monitoring drop-outs). On the other hand, since all of these non-pharmacologic interventions are readily available to the general public, it is equally important to assess dietary and other lifestyle changes in the comparison groups (monitoring drop-ins). For all participants, therefore, compliance means not only following any active regimen that may be assigned; it also means avoiding any alterations in dietary or exercise habits, for example, that are not part of the allocated program.

The data collection schedules for the lifestyle and the supplements interventions are outlined in Tables 2 and 3, respectively. The total duration of Phase 1B is 36 months, which includes a 12-month recruitment and enrollment period as well as a 6-month close-out period. Therefore, for the lifestyle interventions, the duration of follow-up will range from 18-27 months, with an average of 22 months. For the supplements interventions, the total study period will be divided into two sequential testing phases with a 3-month washout period in between. Total follow-up for each sequence will be six months.

All clinics will screen potential participants at three visits (10-30 days apart) to determine eligibility, to eliminate the obvious non-compliers, and to obtain baseline values for variables such as BP and weight. For the supplements interventions, there will be a run-in period and a visit approximately four to eight weeks after SV3 to assess compliance with the pill-taking regimen prior to randomization. In addition, those clinics testing supplements will conduct three visits to re-establish eligibility at the beginning of Stage 2.

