In addition to the behavioral compliance measures that have been described previously, there will be a pre-randomization run-in period for the supplements arm of the trial. The purpose of the run-in is to allow individuals likely to become non-compliant to the study regimens to be eliminated prior to randomization. During the run-in, potential participants will have an opportunity to try a pill-taking regimen similar to that which will be required during the active intervention phases. This strategy has particular applicability to the supplements arm of TOHP, since the use of placebo control and the lack of major side-effects associated with any of the supplements make it possible to test the exact intervention regimen

11/7/88

(i.e., pill taking) prior to randomization without contaminating the study groups.

Magnesium placebo capsules (six per day) will be used for the run-in. Magnesium placebos were chosen because they are relatively large and six is the maximum number of pills per day which a participant will be required to take in either the first or second testing periods. Thus, it is anticipated that participants able to comply with this pill-taking regimen will also be able to comply with any of the other supplement regimens involving fewer numbers and smaller capsules or tablets.

Clinic Procedures

All participants randomized to the supplements arm of the trial will be assigned to a specific health counselor who will see them individually at each intervention visit and who will be responsible for tracking their progress in achieving the study objectives. The nature of the counseling sessions will be tailored to the individual and could include specific instruction regarding the administration of the supplements, positive reinforcement, motivational talks, videotapes and discussion of suspected side-effects.

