a. Prior to Stage 2, individuals with a bleeding history will be identified based upon responses to the Supplements Form administered at SV3, SRV, 6 weeks, 13 weeks, and 26 weeks and reviewed by a clinic physician. Those individuals identified by the clinic physician as having a potential bleeding disorder based upon responses to the follow-up forms, will be asked to undergo evaluatory tests for

bleeding time, platelet count and VWF level for possible exclusion from Stage 2 based upon a history of recurrent abnormal bleeding.

- b. Individuals identified by the clinic physician as having a potential bleeding disorder, who do not wish to submit themselves to testing, will be excluded from Stage 2.
- c. During Stage 2, individuals assigned to the fish oil component who develop a bleeding history based upon responses to the Supplements form administered at 6 weeks and 13 weeks of Stage 2 or other self-reports will have their case reviewed by a clinic physician. If in the judgement of the physician it is clinically warranted, the individual will be asked to undergo tests immediately to evaluate the bleeding problem. Participants will be asked to discontinue their pills for the duration of the trial if, in the opinion of the clinic physician, the tests reveal an abnormal bleeding problem or if the participant refuses to undergo the recommended evaluation procedures.

ASCERTAINMENT OF ENDPOINTS

Both primary and secondary outcomes for TOHP are determined from measurements and laboratory tests taken at follow-up visits; therefore, ascertainment of endpoints is relatively simple and straightforward. Outcome measurements will be made by data collectors blinded to the treatment assignment of participants and not involved in delivering any lifestyle intervention. Due to the subjective nature of BP measurement, it is particularly important that the BP observers are not involved in any way with the delivery of any intervention and have no access to intervention-specific data. Insofar as possible, data collection visits should take place on different days and at different locations from intervention visits so that those in the active intervention groups do not become more habituated to the data collection environment than those in the comparison group.

Ascertainment of Blood Pressure

The outcome of primary interest, for which the sample size and power calculations were performed, is diastolic BP; a major secondary endpoint is

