If the sum of these nine readings is less than 810, the subject will continue in the study as usual. If the sum is less than 855 but greater than 810 mm Hg (90-94 mm Hg), and the sum of at least two of the three sets of three readings is less than 285 but greater than 270 mm Hg (90-94 mm Hg), then specific procedures need to be followed to inform the subject and, with permission. his/her personal physician, of the participant's actual BP readings. The principal investigator or other study physician should call or write to the

participant's physician and explain that this notification does not constitute a referral for treatment, since the literature suggests that treatment in this range is optional, but that we are notifying him/her out of an obligation to keep the physician informed about his/her patient. If possible, the principal investigator should negotiate an agreement with the participant's physician to have the participant stay in the trial on his/her assigned intervention and to have the BP readings for each subsequent visit reported to the personal physician. The participant should be contacted prior to each follow-up visit to determine if s/he has been placed on antihypertensive medication. If so, a missed visit form should be completed. If, at a subsequent visit, the subject has been off medication for at least two months, then full involvement in the study should be encouraged.

For those individuals who go on and off antihypertensive medication during the study, the final decision as to which data to use in analyses will be made at the termination of the trial. Unless contraindicated, participants should be encouraged to remain on their assigned intervention. Specific contraindications would include potassium supplementation for individuals placed on potassium-sparing diuretics, and calcium supplementation for patients placed on thiazide diuretics.

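### Participants at a mean DBP of 90-94 mm Hg who start an antihypertensive are kept on the intervention, but their follow-up visits are recorded as missed, so the non-BP data go uncollected

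*Protocol*

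**What the plan says.** The rule is in Safety Monitoring. It applies when the nine safety readings sum to more than 810 and less than 855, with at least two of the three visit sums between 270 and 285. Such participants are contacted before each follow-up visit about antihypertensive use. For those on a drug: "If so, a missed visit form should be completed". The return condition is that "the subject has been off medication for at least two months, then full involvement in the study should be encouraged". The next paragraph adds: "Unless contraindicated, participants should be encouraged to remain on their assigned intervention". The named contraindications are potassium with potassium-sparing diuretics and calcium with thiazides.

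Three other places bear on this:

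- Randomization (lifestyle clinics) says that after assignment "every effort will be made to obtain complete follow-up information for the duration of the trial".
- The section on final BP measurements for early terminators, under Ascertainment of Endpoints, says that a participant whose physician treats after learning the underlying BP is terminated. The nine readings then become the terminating BP.
- Data Analyses says that leaving such people out would bias the effect estimates, and it plans censored-data methods for their BP.

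**The concern.** A follow-up visit is more than a BP visit. Recording it as missed because BP can no longer be interpreted also gives up data that a new drug does not spoil, or spoils only in part. Some of these are intervention-specific secondary endpoints: urinary sodium, body weight, urinary minerals and serum magnesium. Others are the side-effect form and the review of exclusion conditions, in people who have just added a drug and are encouraged to continue the intervention. Exposure continues while scheduled observation stops.

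Drug starts depend on BP, which the interventions aim to change, so the loss need not be equal between arms. The Protocol gives no rate from which to judge this. Data never collected cannot be recovered in the analysis, although Safety Monitoring leaves until the end of the trial the choice of which data to use for people who go on and off medication.

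**Working it through.** **1. The band.** 810/9 = 90 and 855/9 = 95; 270/3 = 90 and 285/3 = 95. The sums agree with the printed 90-94 mm Hg range. To reach it, a participant first needs a visit mean of at least 93.5 and then a six-reading mean of at least 93.5 (561/6 = 93.5).

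**2. What the replaced visit carries.**

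- Side-effect items and current status on the exclusion conditions, including pregnancy (Safety Monitoring).
- Weight, 24-hour urine and, for supplements, pill count (Follow-Up Schedule, Tables 2 and 3).
- Serum magnesium at 3 and 6 months in the Stage 1 magnesium and control groups (Table 5).

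**3. Whether other text restores these data.** No section reschedules them or describes a partial visit for someone on a drug. The content of the missed visit form is not shown. That the data are not collected is therefore an inference, but it is the ordinary meaning of recording a visit as missed. Postponing full involvement until two months off the drug points the same way.

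**4. Loss per affected person.** Assumptions: the trigger is a scheduled data visit and that visit is kept; the drug starts once the nine readings are complete, at least two weeks later (two returns of at least one week each); a follow-up point is lost if the participant is on the drug or has been off it for less than two months. The last part is inferred from the return condition. A point at month v is then saved only if the drug is stopped by month v - 2: 6 - 2 = 4, 12 - 2 = 10, 18 - 2 = 16.

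Lifestyle points fall at 3, 6, 12 and 18 months, with urines at 6, 12 and 18.

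| Trigger | Stopped by month 4 | After 4, by 10 | After 10, by 16 | Past 16 |
|---|---|---|---|---|
| 3 months | 0 | 1 | 2 | 3 |
| 6 months | n/a | 0 | 1 | 2 |
| 12 months | n/a | n/a | 0 | 1 |

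An 18-month trigger loses none. The same number of urines is lost, so the worst case is 3 of 4 points and 3 of 3 follow-up urines. Separate termination visits after 18 months are not counted.

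Supplements points fall at 3 and 6 months in each stage. A trigger at 3 months loses 0 of 2 if the drug is stopped by month 4, and otherwise 1 of 2, with 1 of 2 follow-up urines. In the Stage 1 magnesium and control groups, 1 of 2 on-treatment serum magnesium tests goes too. No loss at Stage 2 entry is counted, because it is unclear whether the rule applies to people admitted there while on BP-lowering drugs.

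**5. How many people.** This cannot be derived. The Protocol gives neither the share reaching the band nor the share then treated.

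**6. The two rules side by side.** The early-termination section terminates a participant whose physician treats after seeing the nine readings. Safety Monitoring keeps a treated participant on the intervention with a route back. The same person can meet both descriptions, and neither section says which prevails.

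**The case against.** The strongest reply is that nothing says in words that non-BP data stop, and that operational detail sits in a Manual of Operations that is not shown. This stands as a limit on certainty. It does not remove the instruction, which is in the Protocol itself.

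A second reply is that on-drug data are worth little, since diuretics alter urinary electrolytes and antihypertensives can cause fatigue or faintness. That is a reason to flag those values. It does not apply to pill counts or exclusion conditions.

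A third is that if the termination rule governs, the case of someone on the intervention but unobserved largely disappears. That is right, but the advice to stay on the intervention would then have little purpose, which is why the two rules need reconciling.

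Three stronger readings are tempting and are not supported:

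- *The rule breaches uniform data collection.* Follow-Up Schedule says: "Baseline and follow-up data, other than intervention-specific data, will be collected uniformly from all trial participants regardless of treatment assignment". That wording concerns treatment assignment, and the missed-visit rule applies alike in every arm. Any breach is weak; the clearer tension is with the commitment to complete follow-up.
- *Remaining contact is unequal across the trial.* Active and placebo supplements participants alike have "a specific health counselor who will see them individually at each intervention visit", under double blinding, and that counselor discusses side effects. Unequal contact arises only between active lifestyle arms and lifestyle controls. For controls, Study Design says the "group will be invited to the clinic for data collection visits only". They keep a case manager and the call before each visit, but neither is assigned any data collection. Contacts in the active lifestyle arms are no full substitute either, since "Outcome measurements will be made by data collectors blinded to the treatment assignment of participants".
- *The primary result is compromised.* Anyone in the band already has nine readings taken before treatment, and Data Analyses plans to use such readings. Starting a drug also counts as developing hypertension.

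**Conclusion.** The point holds as a limited defect worth correcting. For participants at a mean DBP of 90-94 mm Hg who start an antihypertensive, the Protocol stops scheduled non-BP collection until two months off the drug, on the plain reading of its text, while encouraging them to continue the intervention. The loss runs from 0 to 3 of 4 lifestyle follow-up points, and 0 or 1 of 2 per supplements stage, under the timing assumptions given. The number of people is unknown and probably small. Secondary endpoints, adherence and safety data are affected; the primary DBP comparison is largely protected. Data collected before the drug start remain in the side-effect comparison. Nothing here shows that non-BP follow-up must be extended to participants who are properly terminated under the early-termination section; that would be a separate design choice.

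**What to change.** In Safety Monitoring, replace the missed-visit instruction with these steps:

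1. Hold the scheduled visit and collect all non-BP data: side effects, exclusion conditions, weight, 24-hour urine, pill count and scheduled bloods.
2. Record the drug, its class and its start date.
3. Mark BP, urinary electrolytes and side-effect reports as on-drug. Set marked BP aside in drug-free analyses, and report the side-effect comparison and urine-based adherence analyses with and without marked data.

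Also state that the nine pre-treatment readings stand as the terminating BP, and that the Safety Monitoring rule governs participants in the 90-94 mm Hg band who remain on their intervention or in the control group.

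The cost is small: the wording, three drug items and a flag on the forms. The visits, staff and assays are already planned. The downside is having to handle drug-confounded values and report two analyses both ways.
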